## Direct Benefits to Subjects

Direct Benefits to Subjects

This study was not designed for the direct benefit of the participants.

Participants will be offered three months of treatment visits with a psychiatrist for medication management at the conclusion of the tDCS procedures.

## Compensation and/or Reimbursement

Will compensation or reimbursement for expenses be offered to subjects?

Yes

Please describe and indicate total amount and schedule of payment(s).

Include justification for compensation amounts and indicate if there are bonus payments.

## Sample of patients with NSSI:

**For neuroimaging participants:** Subjects who complete all imaging assessments will be compensated a total of \$150. Subjects who do not complete all imaging assessments will receive a partial payment prorated based on their participation in the study (\$50 for each fMRI scan and \$50 for the tDCS administrations).

---

**For participants without neuroimaging:** Subjects who are enrolled without neuroimaging and complete all clinical assessments will receive \$150.

Payment procedures are initiated upon subject's completion of the study. Payment is in the form of a check, usually received in the mail about 4-6 weeks after completion of the study procedures.

**Sample of healthy volunteers for fMRI pilot:**

Participants in the fMRI portion of the pilot will receive \$50 for each of the two scans at the completion of the scan, for a total of \$100.

## Uploads

Upload copy(ies) of unbolted Consent Form(s)

Upload copy(ies) of bolted Consent Form(s)

Upload copy(ies) of the HIPAA form

HIPAA.pdf

HIPAA\_e\_sign.pdf

Upload any additional documents that may be related to this study

## **STATISTICAL ANALYSIS PLAN**

This is a double-blinded, randomized, sham-controlled pilot study examining the tolerability and effectiveness of repeated administrations of tDCS over right vIPFC in treating NSSI and its underlying neural correlates.

Primary analyses on behavior and clinical outcomes will be conducted using linear mixed effects models to account for repeated measures over time and individual variability. All tests will be performed using two-sided alternatives with alpha=0.05. Ecological momentary assessment data will be evaluated using mixed effects logistic regression. BOLD imaging data will be analyzed using generalized linear models comparing pre- and post- intervention neural responses to inclusion and exclusion trials during the Cyberball game. For all analyses, we will examine standard diagnostic plots to identify evidence of lack of model fit, presence of outliers or overly influential points, etc., and take appropriate remedies as indicated (e.g., review source data of outliers, transform data, etc.).

As this is a pilot study, additional exploratory analyses will be conducted for hypothesis generating purposes.

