
---

thoughts, feelings, and behaviors. This will allow measurement of NSSI urges and behaviors for one week before, one week during, and one week after the tDCS intervention. The long-term goal of this study is to identify a novel form of treatment for NSSI and to better understand NSSI pathophysiology.

A sample of 24 patients who engage in NSSI will also be recruited to evaluate the feasibility of at-home self-administration of tDCS. tDCS delivery using a remotely-supervised treatment protocol will minimize the burden of study visits and allow patients to continue participating in research from the comfort of their homes when in-person procedures are not possible. These participants will undergo similar study procedures as described above for patients with NSSI, except for the MRI scan, in order to explore aims 1 and 3 above in a remote setting. Those in the remote arm of the study will complete an additional week of tDCS sessions, totaling 12 sessions over 6 days. We will continue to offer three months of treatment visits with a study psychiatrist at no-cost at the conclusion of study procedures, which will be provided via telemedicine.

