## Specific Aims and Hypotheses

### Specific Aims and Hypotheses

Aims/Hypotheses 1 through 3 pertain to the sample of patients with NSSI. Aim 4 pertains only to the non-clinical sample who will pilot our social feedback task. Aim 5 pertains to the remotely-supervised no-contact arm of the study.

1. Evaluate the tolerability and acceptability of a tDCS intervention in a sample of individuals engaging in frequent NSSI. We hypothesize that 6 treatments of tDCS (two times per day for three days over right vLPFC) will be well-tolerated by study participants who engage in frequent NSSI.
2. Characterize changes in BOLD responses to social rejection from pre- to post-tDCS sessions in the active tDCS group compared to the sham tDCS group using fMRI and a social exclusion task called Cyberball. Hypothesis: BOLD activity in the dorsal anterior cingulate cortex, the anterior insula, the amygdala, and the medial PFC/rostral ACC will scale with different percentages of exclusion in Cyberball. Furthermore, there will be a significant interaction effect whereby participants in the sham stimulation group will show greater changes in these three regions during scan 2 compared with those in the active group.
3. Gather pilot data on the effectiveness of tDCS in treating NSSI and the urge to engage in NSSI in patients currently suffering from NSSI on a regular basis. Hypothesis: tDCS directed to the right ventrolateral prefrontal cortex will lead to greater reductions in both NSSI and in urges to engage in

NSSI, as assessed by self-report measures as well as real-time monitoring using ecological momentary assessment, than sham tDCS.

4. Assess feasibility of the behavioral and neural responses to a social feedback task in a non-clinical sample.
5. Assess the feasibility of using remotely-supervised tDCS self-administration in a sample of patients who engage in NSSI.

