### Inclusion/Exclusion Criteria

Name the subject group/sub sample

Neuroimaging participants

Create or insert table to describe the inclusion criteria and methods to ascertain them

Neuroimaging participants with NSSI: Inclusion Criteria	Method of Ascertainment
1. Age 18-60	Remote interview
2. Frequent current NSSI (including cutting in which the skin is broken; self-hitting in which there is bruising; or burning in which there is evidence of a burn. Will not enroll if skin-picking or scratching is the only form of self-injury): has engaged in $\geq 2$ episodes of NSSI in the two months prior to enrollment	Remote Self Injurious Thoughts and Behaviors (SITBI) scale and remote clinical interview
3. Capacity to provide informed consent	Remote clinical interview
4. If carries a diagnosis of bipolar I or II disorder, taking or willing to begin a therapeutic dose of a mood stabilizer*	Remote SCID, remote clinical interview, therapeutic blood levels if applicable
5. Normal hearing	Remote interview
6. Physical capacity (e.g., manual dexterity) to set-up and self-administer tDCS	Remote interview

\* If not currently taking a mood stabilizer, the participant will have the option of beginning mood stabilizer with a psychiatrist on our team. We would perform any necessary blood testing to screen for appropriateness of mood stabilizer treatment and to monitor blood levels. We would provide psychiatrist visits and any necessary blood testing, but would not cover the costs of mood stabilizer medication. If participants continue to meet all other eligibility criteria upon achieving a therapeutic dose of mood stabilizer, we would proceed with research participation. If they do not, we would forego research procedures and offer 3 months of open treatment.

Create or insert table to describe the exclusion criteria and methods to ascertain them

Neuroimaging participants with NSSI: Exclusion Criteria	Method of Ascertainment
1. Unstable medical conditions based on medical history or medical assessment	Medical history (by a physician), medical assessment as conducted in IRB #4815
2. Current psychotic disorder, mania, hypomania, intellectual disability	Remote psychiatric interview and SCID
3. Dermatologic condition resulting in non-intact skin on the scalp	Medical history
4. Significant suicidal ideation with a plan and intent that cannot be managed safely as an outpatient	Remote C-SSRS, remote clinical interview

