### **Real-Time Monitoring of NSSI, Stressors, and Urges**

In addition to using retrospective reports of NSSI, we will also employ a recently developed assessment, Ecological Momentary Assessments (EMA). EMA records thoughts, feelings and behaviors and the circumstances preceding these experiences in real time, which may allow for a more accurate understanding of mood and behavior than retrospective reporting (Nock et al., 2009).

In this study, we will use EMA to have participants rate the frequency, duration, and severity of urges to engage in NSSI, the frequency and nature of actual NSSI, as well as suicidal ideation, relevant affects, stressors and behaviors, and possible triggers for these events, for one week prior to treatment, through the duration of the course of tDCS treatments, and one week following completion of tDCS, to measure the persistence of any observed effects. These items will be presented to each participant on an iPod device during each momentary assessment. We will enter each subject's self-reported typical waking and bedtime

---

into the software. Using this information, the program will stratify waking hours into six intervals, then randomly select one moment within each interval to deliver a prompt of an audible beep. This beep will be repeated every 30 seconds for up to 5 minutes. Collected data will be downloaded when the device is synced with a computer and can be easily imported into standard spreadsheets or statistical packages. If the participant records the presence of treatment emergent suicidal ideation, an open-ended question allowing the subject to record descriptions of their experience with this development will be presented. Subjects will also be reminded about emergency procedures to contact staff if they are concerned about suicidal ideation or risk.

We have used this procedure in a NIMH-funded study of actively suicidal patients without adverse effects and with good adherence.

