### **Sample of patients with NSSI:**

Through co-enrollment in IRB #4815, participants will undergo a careful psychological assessment including characterization of DSM-IV diagnoses using the Structured Clinical Interview for DSM-IV (SCID, (First et al., 1995; First et al., 1997)). Recent suicidal ideation and behaviors will be assessed using the Columbia Suicide Severity Rating Scale (C-SSRS), which will be repeated on a weekly basis during tDCS administration to monitor emergent suicidal ideation (Posner et al., 2011). Selected items from the Self-Injurious Thoughts and Behaviors Interview (SITBI) will be used at baseline and on a weekly basis to monitor self-reported frequency, nature, motivations, and effects of NSSI, as well as urges to engage in NSSI, throughout study participation. Selected items from the Non-Suicidal Self-Injury Assessment Tool (NSSI-AT) will also be acquired at baseline to acquire additional information regarding history of NSSI behavior. The Clinical Global Impressions scale (CGI) (Guy et al., 1976) will be conducted on a weekly basis to monitor for clinical worsening. Possible mediators of treatment outcome that will be examined in the study include: emotion regulation using the Difficulties in Emotion Regulation Scale (DERS, (Gratz et al., 2004)) and the Cognitive-Attentional Syndrome Questionnaire (CAS-1; Wells, 2009); engagement with the ATT with the ATT-Scale; trait rumination with the Ruminative Responses Scale (RRS; Treynor et al., 2003) expectancy of clinical benefit, assessed with the Credibility/Expectancy Questionnaire (Devilly et al., 2000); and depression severity, as assessed by the Hamilton Depression Rating Scale (HDRS, (Hamilton, 1960)) and the Beck Depression Inventory (BDI, (Beck et al., 1961)). Tolerability of tDCS will be evaluated using the tDCS Adverse Effects Questionnaire (Aparicio et al., 2016).

Sample of remote-only patients with NSSI: Rater-administrated psychological assessments will be administered by phone or secure video-conference, and participants will be sent a link to complete self-report measures remotely through a secure platform (either REDCap, SIR, or Qualtrix). Cyberball will be remotely administered within one week before the first tDCS session and within one week after the final tDCS session. The original version of Cyberball was administered and validated for use as a digital task outside of the scanner (Williams, Cheung, & Choi, 2000).

Table: Timing of Psychological Assessments

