## **Research Related Delay to Treatment**

Will research procedures result in a delay to treatment?

Yes

Maximum duration of delay to any treatment

Study participants may continue with ongoing psychotherapeutic and/or pharmacologic treatment, as long as it was not started within 8 weeks of study enrollment. For participants not currently receiving psychiatric treatment, there may be a delay of up to 35 days prior to initiating tDCS through the study, in order to schedule baseline assessments, MRI scanning. For patients with bipolar 1 or 2 disorder not on a therapeutic dose of a mood stabilizer, evidence-based treatment with mood stabilizer treatment will be offered that would begin within 3 weeks of enrollment; tDCS research procedures would be further delayed in this case for the purposes of achieving a therapeutic dose of a mood stabilizer (prioritizing this clinical treatment ahead of research procedures).

Maximum duration of delay to standard care or treatment of known efficacy

Eight weeks

Treatment to be provided at the end of the study

One week following the conclusion of tDCS procedures, open medication-based treatment will be offered to study participants for a period of three months.

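### The SAP does not say how baseline NSSI enters the Aim 3 models; the usual arm-by-time form would lose precision that adjusting for the baseline week recovers at almost no cost

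*Combined protocol and SAP*

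**What the plan says.** The SAP gives one sentence to clinical outcomes: "Primary analyses on behavior and clinical outcomes will be conducted using linear mixed effects models to account for repeated measures over time and individual variability". It gives another to EMA: "Ecological momentary assessment data will be evaluated using mixed effects logistic regression". Tests are two-sided at 0.05. No fixed effects, contrast, baseline term or follow-up window is named.

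Aim 3 (protocol, Specific Aims and Hypotheses) predicts that active stimulation "will lead to greater reductions in both NSSI and in urges to engage in" NSSI than sham.

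NSSI is measured in two ways:

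- **SITBI.** Selected items "will be used at baseline and on a weekly basis to monitor self-reported frequency, nature, motivations, and effects of NSSI" (Assessment Instruments). No recall window is given. The timing table lists enrollment, baseline, post-final session, one week post-treatment and four-week follow-up, with no weekly column.
- **EMA.** The Lay Summary says: "This will allow measurement of NSSI urges and behaviors for one week before, one week during, and one week after the tDCS intervention". The Real-Time Monitoring section instead runs EMA through the whole tDCS course, plus one week on each side.

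Entry requires at least two "episodes of NSSI in the two months prior to enrollment". Eligibility is the only stated use of that history.

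**The concern.** The entry threshold is low, so a single week is a poor measure of a person's NSSI rate. Under the rates assumed below, 43% of participants would have a zero baseline week. Subtracting so noisy a value adds its error to the outcome, whereas adjusting for it does not.

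The SAP's wording permits both. A reduction is commonly coded as arm-by-time, and that is the less efficient form. With 22 completers planned in the imaging sample and 24 in the remote sample, precision is scarce, and the pilot is meant to inform larger trials. Leaving the choice open also means that it could be made after the data are seen.

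**Working it through.** The plan gives no variance, correlation, rate or power figure for NSSI, so there is nothing of its own to reproduce. All sizes below rest on assumptions.

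**1. What the usual model estimates.** Simulated data with a baseline-to-outcome correlation of 0.4 were analyzed in four ways. Variances of the treatment estimate:

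| Analysis | Variance |
|---|---|
| Mixed model, unconstrained arm-by-time | 0.2001 |
| Difference in change scores | 0.2001 |
| Mixed model, common baseline mean | 0.1364 |
| ANCOVA on baseline | 0.1385 |

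The first two estimates agreed to within 1e-14. The ratio of the first to the third is 0.2001/0.1364 = 1.47.

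**2. Formula.** With equal variances and baseline-to-outcome correlation r, Var(change)/Var(adjusted) = 2(1−r)/(1−r²) = 2/(1+r). This gives 1.67 at r = 0.2, 1.43 at 0.4 and 1.18 at 0.7. It cannot exceed 2 for non-negative r. Larger ratios need an outcome less variable than the baseline week, from averaging several follow-up weeks or from a fall in rate.

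**3. Simulation of the design.** Assumptions: personal rates gamma (shape 1.5, mean 8 per two months), Poisson counts, entry at two or more in 61 days, 11 per arm, 1:1 allocation, one baseline week. Drift multiplies the rate after enrollment by a lognormal (log SD 0.6). Drift is plausible because for some participants "there may be a delay of up to 35 days prior to initiating tDCS through the study". Variance of change divided by variance adjusted for the baseline week alone:

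| Follow-up | Rate ratio 0.5: no drift / drift | No effect: no drift / drift |
|---|---|---|
| Two weeks | 2.33 / 2.09 | 1.68 / 1.54 |
| Three weeks | 2.75 / 2.25 | 1.98 / 1.57 |

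A second run of this model gave 1.5 to 2.6 for two or three weeks and 1.3 to 1.8 for one. The gap at the top (2.75 against 2.6) is about what simulation error allows. The working range is therefore 1.3 to 2.6. In standard errors this is √1.3 = 1.14 to √2.6 = 1.61. In precision, 22 participants analyzed as change are worth about 22/1.3 = 17 down to 22/2.6 = 8 to 9 analyzed with adjustment.

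**4. Longer SITBI baseline.** If the baseline item covers four weeks, the ratio for the same covariate is 1.11 to 1.64.

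**5. EMA logistic model.** Assuming 34 answered prompts a week (of 6 × 7 = 42), a common baseline reduces the variance of the log odds ratio by a factor of 1.4 to 2.0 relative to treatment-by-phase. With two baseline covariates, large-sample likelihood-ratio tests rejected a true null in 7 to 10% of runs, against 4 to 6% for treatment-by-phase.

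**6. Cost of one covariate.** The variance inflation is 1 + 1/(N−4): 1 + 1/18 = 1.06 at N = 22 and 1 + 1/20 = 1.05 at N = 24. The ratios in step 3 already include it.

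**7. Enrollment count as an extra covariate.** With drift and three follow-up weeks, adding the log count moves the ratio from 2.25 to 2.29 (rate ratio 0.5) and from 1.57 to 1.68 (no effect). Used alone it gives 1.46 and 1.08. At a mean of 40 with drift and no effect it gives 0.28, far worse than the change score.

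**The case against.** The strongest reply is that the fault is conditional. The SAP never states a change analysis, and a mixed model with a common baseline mean would satisfy its wording. That stands. A reader might infer from Aim 3 that change from baseline is the planned analysis, but the aim states a hypothesis, not a model. What remains is that the efficient form is not specified and the common default is the inefficient one.

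A reader might also infer a loss of three- or fourfold. The documents do not support that as a headline. In the base model, ratios above 3 needed three pooled weeks, a halved rate, no drift and the enrollment count as a second covariate. A one-week baseline is documented only for EMA, which goes to logistic regression; the SITBI window is not stated.

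It may seem to follow that the enrollment count should be a required covariate. It adds almost nothing once rates drift, and no passage confirms that an exact number is recorded.

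Nor does it follow that logistic regression is wrong for graded EMA urges. On an assumed 0-10 scale, the gain from a graded analysis was −1 to 9 points of power, too uncertain to press.

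Finally, Aim 3 only gathers pilot data. That is fair. At 11 per arm, the standardized difference detectable with 80% power is (1.96 + 0.84) × √(2/11) = 1.19. Even in the favorable case of three follow-up weeks, a halved rate and both covariates, power was 42%.

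**Conclusion.** The concern holds in conditional form. The SAP leaves baseline handling open. If it is filled in with an unconstrained arm-by-time term, the Aim 3 estimate has about 1.3 to 2.6 times the variance of one adjusted for the baseline week.

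That range rests on the assumed rates, a one-week baseline and complete data, and it is not a bound. Strong overdispersion or very low rates gave up to about 3.6 for the baseline week alone. High rates with drift and no effect gave 1.17. A four-week SITBI baseline gave 1.1 to 1.6. Adjusting for the baseline week was more precise than change in all of these runs. The benefit is a tighter pilot estimate and one fewer choice left until after the data are seen. It does not make the trial well powered.

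**What to change.** In the SAP:

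1. State that arms are compared on post-baseline NSSI with the baseline-period value of the same measure as a covariate. Alternatively, state that the mixed model constrains the arms to a common baseline mean; with complete data and unstructured covariance the two give the same estimate.
2. State the follow-up window. Reconcile the two descriptions of EMA duration and the weekly SITBI wording with the timing table, and give the SITBI recall period. Open treatment is offered from one week after tDCS, so say whether the four-week visit counts toward this comparison.
3. Use the same baseline handling in the EMA logistic model for NSSI. If a covariate is used there, use a permutation or other small-sample test.
4. Optionally, add the log enrollment two-month count as a second covariate if it is recorded as an exact number. It should never be the only covariate.

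The cost is SAP wording, one degree of freedom (about 5 to 6% in variance if the covariate carries no information) and slightly more analysis work. Visits, treatment and sample size are unchanged.

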The primary aim of this study is to examine the tolerability and effectiveness of tDCS in treating NSSI and urges to engage in NSSI. For this experiment in which we are examining the effects of anodal vLPFC tDCS on NSSI behavior and the neural correlates of social rejection assessed by fMRI, we plan to enroll up to 50 individuals who engage in frequent NSSI to obtain a sample of 23 subjects who complete the study procedures. Participants will be randomized to receive active anodal vs. sham tDCS to right vLPFC for two twenty-minute applications on each of six alternating days over approximately two weeks. During the stimulation, participant behavior will be standardized by having all participants engage in the same Attention Training Technique administered over headphones. NSSI behaviors and urges will be recorded for three weeks using Ecological Momentary Assessment (EMA), a novel procedure that minimizes recall bias by capturing the thoughts, feelings, and behaviors of subjects in real time. This will allow measurement of NSSI urges and behaviors for the weeks before, during, and after the tDCS intervention. Our first goal in this study is to characterize tolerability and acceptability of this intervention in this population. Secondly, we wish to identify changes in BOLD responses to social rejection from pre- to post-tDCS using fMRI. We hypothesize that activity in the AI, dACC, and amygdala during rejection will be attenuated by tDCS. Lastly, it is hypothesized that tDCS directed to the right vLPFC will lead to reductions in both NSSI and in urges to engage in NSSI. This pilot work may pave the way for larger controlled trials to examine differential target engagement and clinical efficacy between active and sham conditions.

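### The SAP's only BOLD sentence states a pre-versus-post contrast with no arm, while Aim 2 asks for an active-versus-sham difference in change; the plan should name the arm-by-scan test

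*Combined protocol and SAP*

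**What the plan says.** The Statistical Analysis Plan has one sentence on imaging: "BOLD imaging data will be analyzed using generalized linear models comparing pre- and post- intervention neural responses to inclusion and exclusion trials". No other section gives an imaging model. The SAP's opening sentence describes the study as randomized and sham-controlled, but no model sentence in it carries an arm term. All tests are two-sided at 0.05.

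Aim 2, under Specific Aims and Hypotheses, is to "Characterize changes in BOLD responses to social rejection from pre- to post-tDCS sessions in the active tDCS group compared to the sham tDCS group". Its hypothesis is that "there will be a significant interaction effect whereby participants in the sham stimulation group will show greater changes in these three regions during scan 2". The regions named just before are "the dorsal anterior cingulate cortex, the anterior insula, the amygdala, and the medial PFC/rostral ACC", which is four. Aim 2 also expects BOLD activity to scale with the degree of exclusion, and the Cyberball section varies the degree of exclusion from block to block.

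The Background, Significance and Rationale section is worded differently: "Secondly, we wish to identify changes in BOLD responses to social rejection from pre- to post-tDCS using fMRI". It continues: "We hypothesize that activity in the AI, dACC, and amygdala during rejection will be attenuated by tDCS". It closes with: "This pilot work may pave the way for larger controlled trials to examine differential target engagement and clinical efficacy between active and sham conditions".

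**The concern.** The comparison stated in the SAP is not the one stated in the aim. Time and trial type appear in the SAP sentence; arm does not. The Background does not settle the matter, since it also frames the imaging goal as pre-to-post change and mentions the active-versus-sham contrast in connection with later trials.

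The choice matters because both arms share influences other than current. Participants do Cyberball at both scans (Lay Summary; Aim 2; Cyberball section), so habituation or familiarity can move the second scan. During stimulation, "participant behavior will be standardized by having all participants engage in the same Attention Training Technique", so any effect of that training is present in both arms as well. A pre-post comparison cannot separate these from tDCS. The randomized sham arm can, provided arm is in the test.

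**Working it through.** **Inputs from the documents.** 22 imaging completers (Description of Subject Population, Sample #4; the Background says 23); two scans; random assignment to active or sham, ratio not stated; two-sided alpha 0.05. The documents give no effect size, SD or power for BOLD, so there is no planned figure to reproduce.

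**Assumptions.** 1:1 allocation (11 per arm); change scores with SD 1; a shift *c* common to both arms; a tDCS effect *δ* in the active arm only. The values of *c* are not from the documents.

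**What each contrast estimates.**
- Active arm, pre-post: *c* + *δ*
- Both arms pooled, pre-post: *c* + *δ*/2
- Arm-by-scan interaction, (active change) − (sham change): (*c* + *δ*) − *c* = *δ*

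Only the third is free of *c*. With two scans it is the same as a two-sample comparison of change scores.

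**Rejection rates with *δ* = 0.** For the pre-post tests, a one-sample t test on change with noncentrality *c*√n:

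| Common shift *c* (SD) | Pooled, n = 22: noncentrality | Pooled: rejects | One arm, n = 11: rejects | Interaction: rejects |
|---|---|---|---|---|
| 0 | 0 | 5% | 5% | 5% |
| 0.3 | 0.3 × 4.690 = 1.41 | 27% | 15% | 5% |
| 0.5 | 0.5 × 4.690 = 2.35 | 61% | 32% | 5% |
| 0.8 | 0.8 × 4.690 = 3.75 | 95% | 67% | 5% |

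Simulation with 100,000 runs per scenario agreed for the pooled test (0.271, 0.612, 0.946 at the three non-zero shifts) and for the interaction (0.049 to 0.051). With 23 completers the pooled figures are 28%, 63% and 96%.

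If each arm were tested separately, the chance of a significant active arm and a non-significant sham arm is p(1 − p):
- 0.147 × 0.853 = 0.125
- 0.323 × 0.677 = 0.219
- 0.668 × 0.332 = 0.222

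**Precision of the interaction test.**
- Standard error, 11 per arm: √(2/11) = 0.426 SD of change.
- 95% CI half-width: t(0.975, 20) × 0.426 = 2.086 × 0.426 = 0.89 SD.
- Difference detectable with 80% power (noncentral t): 1.26 SD. The normal approximation gives (1.960 + 0.842) × 0.426 = 1.19 SD.
- Power at a true difference of 0.5 SD: 20%; at 0.8 SD, 43%; at 1.0 SD, 61%.
- With 12 and 11 (23 completers): half-width 2.080 × √(1/12 + 1/11) = 0.87 SD; detectable difference 1.23 SD.

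**The case against.** The best reply is that this is one combined document and Aim 2 states the comparison outright, with an interaction. The SAP calls the study sham-controlled. An interaction is itself a comparison of pre-post differences, so the SAP sentence does not exclude it. That stands. A reader might infer that the planned analysis will fail to answer Aim 2, or that the between-arm test has been abandoned. The text does not support either; it supports only that the term is unstated and that a literal reading might miss it.

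A reader might also take the Background as postponing the active-versus-sham comparison. It says only that the pilot may lead to larger trials of that question, and the same section randomizes participants to active or sham.

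Nor is the direction of the predicted effect missing. The Background says tDCS will attenuate activity. Aim 2's prediction of greater changes under sham sits awkwardly beside that and could be reworded to agree, but the tests are two-sided, so the test is unaffected.

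The illustration is open to two fair criticisms. No section proposes a pooled, single-arm or separate-arm test, and the shifts are invented. The 5% for the interaction also applies to one test: three independent regional tests would give 1 − 0.95³ = 14%. Both stand, and the rejection rates should not be read as this trial's error rates.

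Finally, the omission is not peculiar to imaging. The clinical and EMA sentences name no arm either, although Aim 3 predicts greater reductions than under sham. Those sentences give only a model type, whereas the BOLD sentence gives a contrast that differs from its aim.

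**Conclusion.** The concern holds in a limited form. The SAP's stated BOLD contrast is pre versus post without arm, Aim 2's is active versus sham on the change, and the Background leaves the two unreconciled. Pilot status may excuse low power, but it does not justify leaving open which contrast tests a stated hypothesis.

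The size of the risk cannot be computed from the documents. It depends on how far both arms shift between scans, which is unknown: with no shift the pooled and single-arm pre-post tests also reject at 5%, and the 27%, 61% and 95% figures apply only under the assumed shifts and a pooled test. The conclusion that only the between-arm contrast isolates a tDCS effect does not depend on those figures.

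This should be fixed before the imaging data are analysed. The region count (four listed, then called three; the Background lists three) is a wording correction of less weight.

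**What to change.** In the SAP, state that the Aim 2 BOLD test is the arm-by-scan interaction, or equally the scan-2 response compared between arms with adjustment for the scan-1 response. The investigators should name the exclusion contrast it is applied to, consistent with Aim 2's graded exclusion rather than only inclusion versus exclusion. Report the between-arm difference with its 95% CI, and label within-arm pre-post changes as descriptive.

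Align the imaging goal in the Background with this. Use one region list for the interaction in the Background and Aim 2. Reword Aim 2's prediction so that it agrees with attenuation by tDCS. In the same edit, name the arm-by-time term in the clinical and EMA models, since Aim 3 also compares with sham.

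The cost is wording in three sections and the IRB approval that the data and safety monitoring plan requires for amendments. Scans, visits and participants do not change. The price is the precision shown above: with an interval of about ±0.89 SD, a non-significant interaction is not evidence of no effect, and the SAP should say so.
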